## **BACKGROUND**

### **1. Neurodevelopmental outcomes of premature infants**

Improved survival of premature infants has generated intense interest in the quality of life of the survivors. Premature infants have under-developed lungs, brains, digestive tracts, and immune systems. Neurological outcomes for these infants include brain injury (intraventricular hemorrhage, periventricular leukomalacia), blindness, deafness, chronic lung disease, developmental and motor delays and cerebral palsy. The incidence of each of these adverse outcomes increases as infants are born more prematurely. Complicating factors, such as respiratory distress syndrome also has a negative impact on these outcomes. Lower socioeconomic status (SES) also has a marked negative impact, with the risk of abnormal neurodevelopmental outcomes being significantly increased in families with lower SES.

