### **3. How does iNO therapy affect neurodevelopmental outcome in preterm infants?**

In our previous single center, double-blind, randomized, placebo controlled study of 207 infants, we

Principal Investigator: [name]

demonstrated that iNO decreases the rate of abnormal neurodevelopmental outcome in infants with birth weights <2000g receiving ventilator therapy for RDS. Our population group was predominantly African-American of low socioeconomic status. The original intent of this study was to assess role of iNO in decreasing death and chronic lung disease (a complication of prematurity and the need for mechanical ventilation). Nitric oxide was given at the dosage rate of 10 parts per million (ppm) for 12-24 hrs, then 5 ppm for up to 7 days, or until extubation. Infants were also randomized to receive either conventional ventilation or high frequency oscillatory ventilation (HFOV), a popular ventilatory approach believed by some to decrease chronic lung disease. We found no differences in the incidence of chronic lung disease and death between the groups receiving one of the two types of ventilator therapy. Our study concluded that nitric oxide in premature infants with respiratory distress syndrome decreased the incidence of chronic lung disease and death, consistent with our primary hypothesis. We also found that infants treated with iNO also had a markedly decreased incidence of the primary neurological complications of prematurity – serious bleeding in the brain (intraventricular hemorrhage) and strokes in the white matter of the brain (periventricular leukomalacia or PVL).

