## **RESEARCH PLAN**

**Overall Experimental Plan:** The study is a single-site, randomized, double-blind, placebo-controlled trial of inhaled nitric oxide therapy in all preterm infants with any respiratory disease who weigh <1500g at birth. The trial is designed to treat these infants with nitric oxide from birth to 33 weeks gestation – a critical period of brain development in preterm infants. Our primary objective is to compare neurodevelopmental outcomes between our iNO and placebo-treated patients. We also wish to study the mechanisms underlying the protective effect of iNO, by assessing the relationship between nitric oxide delivery to tissues and neurodevelopmental outcome.

The major differences between this study and our previous study are:

- 1) Inclusion of all preterm infants requiring at least supplemental oxygen therapy. Approximately half of all infants weighing <1500 at birth do not require mechanical ventilation with a breathing machine, which was one criterion for inclusion in our previous study. However, these infants are still at risks for abnormal neurodevelopmental outcomes. By including all infants requiring at least supplemental oxygen by nasal cannula, we hope to obtain information regarding the potential beneficial effects of iNO applicable to the majority of at-risk preterm infants.
- 2) Gestational age-dependent duration of iNO therapy. In our previous study, infants were treated with iNO or placebo for 7 days (if still on mechanical ventilation). Consequently, infants received iNO therapy during different periods of brain development: for example, infants of 24 weeks gestation (16 weeks early) received iNO during a period during brain cells were being rapidly produced, while infants of 30 week's gestation received iNO after brain cells had been made and were now forming connections. In this study, our goal is to provide iNO during the entire time the premature brain is developing outside the womb. Therefore, infants will be treated from birth until 33 weeks gestation, so that less mature infants will be treated for a longer time.

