- 3) Specific design of the study to assess neurodevelopmental outcome. Our previous study had been designed to assess the effect of iNO treatment on the incidence of chronic lung disease and death; we assessed these infants' neurodevelopmental outcomes because of our unanticipated finding of decreased brain bleeding and softening. This study has as its primary outcome the incidence of abnormal neurodevelopmental outcome.
- 4) Laboratory-based Specific Aim to assess the mechanisms of the iNO-induced neuroprotection.

**Specific Aim #1. Assess the role of iNO therapy on neurodevelopmental outcome in all oxygen-dependent premature infants having birth weights < 1500g.**

(i) *Rationale.* We have previously found that brief (1 week) treatment of ventilated preterm infants reduces abnormal neurodevelopmental outcome. Because brain development continues throughout gestation, we hypothesize that iNO therapy will be protective to the preterm brain if given from birth until the risk for abnormal neurodevelopmental outcome is similar to that of term infants.

(ii) *Study design.* We have designed a randomized, placebo controlled, double blind study of iNO therapy during Intensive Care Nursery stay, followed by blinded neurodevelopmental assessment at 18 months corrected age, a commonly used developmental endpoint.

(iii) *Patients.* All premature infants cared for in the Intensive Care Nursery at the University of Chicago Medical Center, who are less than 72 hours old, weighing less than 1500 grams at birth, and requiring any respiratory support, will be eligible for the study. Enrolled infants are anticipated to have the same demographics as we have previously reported: 52% male, 70% African-American, 45% single parent household. Potential subjects will be identified and informed consent sought, if possible, prior to birth, otherwise, within the first 3 days after birth.

(iv) *Exclusion criteria.* Those infants with severe congenital anomalies, including major congenital heart disease, or major kidney, lung or brain malformations will be excluded, as will be those infants with a genetic syndrome. Infants judged by the physician to not be viable will be excluded from the study, as will extremely sick infants requiring very high ventilatory pressures (Oxygen Index  $\geq 20$ ). This latter group is excluded because of a previous study by Van Meurs which showed that infants in this category are made worse by inhaled nitric oxide.

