(ix) *Sample size.* In our previous study of infants with RDS, iNO treatment cut the risk of abnormal neurodevelopmental outcome by half. The baseline incidence of abnormal neurodevelopmental outcome is 40% in this age group by published NICHD data. Therefore to see a decrease of abnormal neurodevelopmental outcome to 20% (half of baseline incidence) with 80% power, 82 babies are needed in each arm of the study, for a total of 164 babies. We have previously published an overall mortality rate for intubated infants < 2000g in our nursery of 23%. Because we are including non-intubated infants, we

estimate a mortality rate of about 18%. Therefore, to ensure sufficient infants surviving to follow up, we anticipate needing to enroll approximately 215 babies over 18 months. With a historic 80% follow-up rate, we will need a total of 268 infants. Every year we admit approximately 175-200 infants with birth weights < 1500g. We therefore anticipate enrollment taking as long as 18 months. Our non-consent rate historically is < 10%.

(x) *Standards of neonatal intensive care.* Because we have shown no effect of ventilatory strategy on neurodevelopmental outcome, there will be no external control of ventilatory modality. Because this is a single-site study, variability in practice exists only between our eight member group of neonatologists, with constant care provided by nurse practitioners, residents, and nursing staff.

(xi) *Safety monitoring.* As per our clinical routine, methemoglobin is regularly monitored with arterial blood gases. Although we and others have shown that iNO therapy is safely used in preterm infants, interim safety analyses will be performed when 50% of patients enrolled. Deaths will be compared, as will the incidence of severe intraventricular hemorrhage, and tests of significance made with Chi-square. The study will be stopped if the incidence of either index in the iNO groups is significantly higher than in placebo groups.

(xii) *Primary Outcome.* As we have published, we will measure abnormal neurodevelopmental outcome at 18 months corrected age. Three disability levels will be assessed: disability (cerebral palsy, blind in both eyes, or deaf in both ears); delay (score on Mental or Psychomotor Developmental Index of the Bayley Scales of Infant Development < 70 without a disability) or normal (without disability or delay).

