(xiii) *Secondary Outcomes.* Other neurodevelopmental outcomes to be measured include the incidences of disability or delay; mean cognitive (MDI) and psychomotor (PDI) function scores will be obtained and infant growth charted. Important clinical diagnoses known to affect the risk of adverse neurodevelopmental outcomes will be tracked: respiratory distress syndrome, bronchopulmonary dysplasia, necrotizing enterocolitis, intraventricular hemorrhage (with grade), periventricular leukomalacia, retinopathy of prematurity, and failed hearing screen. Finally, detailed clinical data will be tracked on a daily basis, including fluids, ventilatory status, blood gases, feedings, etc.

(xiv) *Measures to ensure long-term neurodevelopmental follow-up.* The very high follow-up rates we have previously published require intensive efforts of a number of teams following a patient's discharge, including social services and the research staff. All preterm infants will be followed in our high risk follow-up clinic. This clinic is unusual, in that it provides routine, well-child care to its babies, as well as subspecialty care and neurodevelopmental care. Providing routine care provides an important incentive to parents to come to clinic, since they only have one appointment to make. In addition, we provide regular reminders of the role of the University of Chicago Medical Center in the lives of our families: patients receive holiday and birthday cards, and personalized invitations to our regular patient reunions. Finally, families who come for follow-up visits are given gifts and their travel expenses are reimbursed. Families are rewarded at a 9 month follow-up visit and at the 18 month follow-up visit. With this approach, our drop-out rate is less than 15% -- very low for this population by published reports.

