(xv) *Assessment of neurodevelopmental outcome.* As we have previously published, at 18 months post conceptional age, developmental screening with Bayley exams will be performed in our High Risk Follow-up Clinic by [name], who will also perform neurological examinations to identify those infants with cerebral palsy. Other assessments will include measurements of physical growth and review of routine visual and hearing examinations to determine blindness or deafness. Questionnaires assessing socioeconomic status and self report of racial ethnicity will be administered. All examiners will be unaware of treatment regimen assignment. In our previous studies, our follow-up rate of >80% is very high by published standards, especially for an inner city community such as we serve. We anticipate that rate will continue for the current study.

(xvi) *Data analysis.* As we have previously published, data will be analyzed as "Intent to Treat." . Clinical and demographic variables between groups will be compared with Fisher's exact test for categorical variables and Wilcoxon rank-sum tests for continuous variables. Primary outcomes will be analyzed with generalized linear models to obtain relative risks of primary outcome in the two groups. Effects of potential confounders will be adjusted for in the model: birth weight, sex, socioeconomic status, as well as for potential the intermediate variables: prolonged exposure to postnatal steroids, presence of chronic lung disease, severe IVH, or periventricular leukomalacia (PVL). Further analyses of Bayley scores, both cognitive (MDI) and psychomotor (PDI) will be performed.

(xvii) *Anticipated results and critique.* We anticipate that infants treated with iNO will demonstrate significantly decreased incidences of abnormal neurodevelopmental outcomes and will also demonstrate significantly increased cognitive abilities, as demonstrated by MDI scores. We further anticipate that these effects will persist after statistical adjustment for factors independently predisposing to abnormal neurodevelopmental outcome, such as male gender and gestational age, as well as adjustment for factors potentially mediating adverse neurodevelopmental outcome, such as chronic lung disease, intraventricular hemorrhage, or PVL.

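### The primary model and the randomisation strata contain no measure of lung disease at entry, although the plan calls RDS prognostic; the loss is a little precision, not bias

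*Combined protocol and SAP*

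**What the plan says.** All references are to the combined protocol and SAP.

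- **RDS is called prognostic twice.** Background 1: "Complicating factors, such as respiratory distress syndrome also has a negative impact on these outcomes". Specific Aim #1 (xiii), under the title Secondary Outcomes: "Important clinical diagnoses known to affect the risk of adverse neurodevelopmental outcomes will be tracked: respiratory distress syndrome", followed by bronchopulmonary dysplasia, necrotizing enterocolitis, intraventricular hemorrhage and others. No definition or time of diagnosis is given for RDS.
- **The population is wider than before.** Background 3 describes the earlier trial as one in "infants with birth weights <2000g receiving ventilator therapy for RDS", and (ix) refers to it with "In our previous study of infants with RDS". The Overall Experimental Plan describes this trial as one of "inhaled nitric oxide therapy in all preterm infants with any respiratory disease". Under (iii), infants "who are less than 72 hours old, weighing less than 1500 grams at birth, and requiring any respiratory support, will be eligible". The Overall Experimental Plan adds that about half of infants under 1500 g "do not require mechanical ventilation with a breathing machine, which was one criterion for inclusion in our previous study".
- **The analysis model has no respiratory measure from entry.** Section (xvi): "Effects of potential confounders will be adjusted for in the model: birth weight, sex, socioeconomic status". It then adds four intermediates: prolonged postnatal steroids, chronic lung disease, severe IVH and PVL.
- **The strata are birth weight only.** Section (v) uses five 250-gram bands.
- **Group comparison.** Section (xvi) compares clinical and demographic variables between groups but states no action if they differ.

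**The concern.** In the earlier trial every infant was ventilated for RDS, so an RDS term had little to explain. The follow-up of that trial (Background 3) adjusted for birth weight, gender, postnatal steroids, IVH/PVL and chronic lung disease. The present list is nearly the same, with socioeconomic status added. The entry criteria have since been widened from ventilated infants to those on any support, nasal cannula included, so the respiratory state at entry can now differ from infant to infant, and the model has not followed.

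Chronic lung disease, which is in the model, does not fill the gap because it develops after randomisation. Two things are at stake: some precision in the primary relative risk, and a clear separation between what infants bring to the trial and what treatment might change. Listing RDS beside bronchopulmonary dysplasia and IVH, with no time of diagnosis, blurs that separation.

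**Working it through.** **Inputs from section (ix).** Abnormal outcome 40% on placebo and 20% on iNO; 80% power; 82 infants per arm. Alpha and sidedness are not stated; two-sided 5% is assumed.

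**Step 1: the plan's own figure.** n = [1.96 × √(2 × 0.3 × 0.7) + 0.8416 × √(0.4 × 0.6 + 0.2 × 0.8)]² / 0.2² = (1.270 + 0.532)² / 0.04 = 81.2, so 82 per arm. The stated figure is reproduced; power at 82 is 80.4%.

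**Step 2: assumptions.** The documents give neither the RDS prevalence q nor the risk ratio r for abnormal outcome with RDS against without. I take q = 50%, 70%, 90% and r = 1.25, 1.5, 2, 3, with iNO halving the risk in both groups. Placebo risks are p0 = 0.40 / (q × r + 1 − q) without RDS and p1 = r × p0 with it. The formulas apply to any binary baseline measure, including ventilated or not.

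**Step 3: variance of the risk difference, times n per arm.**
- Unadjusted: 0.24 + 0.16 = 0.40.
- Adjusted: the average within-group variance over both arms, plus half the variance of the group-specific effects.

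Example with q = 0.5, r = 2: p0 = 0.267, p1 = 0.533. Within-group part = 0.5 × (0.2489 + 0.1956) + 0.5 × (0.1956 + 0.1156) = 0.3778. Effect part = (0.5 × 0.267² + 0.5 × 0.133² − 0.04) / 2 = 0.0022. Total 0.380, and 0.380 / 0.40 = 0.95: a 5% reduction.

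**Step 4: chance imbalance.** The 95% limit for the between-arm difference in RDS is 1.96 × √(2q(1−q)/82), ignoring the birth-weight strata: 15.3, 14.0 and 9.2 points at q = 50%, 70% and 90%. At that limit the risk difference shifts by the imbalance times the mean over arms of the RDS risk difference. In the example this is 0.153 × (0.267 + 0.133)/2 = 3.1 points.

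| RDS prevalence | Variance reduction, r = 1.25 / 1.5 / 2 / 3 | Shift at 95% imbalance limit (points) |
|---|---|---|
| 50% | 0.6% / 1.8% / 5.0% / 11.2% | 1.0 / 1.8 / 3.1 / 4.6 |
| 70% | 0.4% / 1.3% / 3.3% / 6.6% | 0.9 / 1.6 / 2.5 / 3.5 |
| 90% | 0.2% / 0.5% / 1.1% / 2.1% | 0.6 / 0.9 / 1.4 / 2.0 |

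The planned difference is 20 points and its unadjusted standard error is √(0.40/82) = 7.0 points.

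**Step 5: these are one loss, not two.** In the example the standard deviation of the shift is 3.06 / 1.96 = 1.56 points. Then 1.56² / 6.98² = 2.44 / 48.8 = 5.0%, exactly the variance reduction in Step 3. The chance imbalance is already inside the unadjusted standard error.

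**Step 6: power.** Simulation of 2000 trials per scenario at 82 per arm, using a Poisson model with robust standard errors:

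| q, r | Unadjusted | With RDS term |
|---|---|---|
| 50%, 1.5 | 79.1% | 79.5% |
| 50%, 2 | 80.3% | 81.9% |
| 50%, 3 | 79.2% | 84.0% |
| 70%, 2 | 79.3% | 80.2% |
| 90%, 2 | 78.9% | 79.2% |

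Four of the five gains are under 2 points; the largest is 4.8. Each power has a simulation standard error of about √(0.8 × 0.2/2000) = 0.9 points, but both analyses use the same simulated data. None of these figures allows for overlap with birth weight, which is both a stratum and a covariate and would shrink them.

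**The case against.** The strongest reply is that the plan already prespecifies three baseline covariates, including the stratification factor, and that adding a fourth is a matter of preference with little return. On size, that is right.

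Three stronger readings are tempting, and the documents do not support them.

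- **That RDS is an entry condition of this trial.** It defined the earlier trial's population. Here eligibility rests on age, birth weight and any respiratory support. RDS would often be evident within the 72-hour window, but that is inference. Consent may precede birth, treatment is described as starting from birth, and no diagnosis time is set, so a tracked RDS diagnosis could post-date study gas.
- **That the omission biases the result or leaves a separate error uncorrected.** Leaving a baseline covariate out of a randomised comparison causes no bias on average, and Step 5 shows that chance imbalance and lost precision are the same quantity. Stratifying on and adjusting for birth weight probably also absorbs part of any imbalance in lung disease.
- **That a between-arm difference in RDS would be reported as an iNO effect.** Section (xiii) describes these diagnoses as risk factors to be tracked, beside fluids and feedings. The heading is loose, but nothing says such a difference will be read as efficacy.

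What remains is that the plan names a prognostic respiratory condition, widens the population over which respiratory disease can vary, and uses no entry measure of it.

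**Conclusion.** The point holds as a minor improvement. Neither the primary model nor the strata use any measure of respiratory disease at entry, and RDS sits under Secondary Outcomes with no time of diagnosis. The randomised comparison remains valid. The cost is roughly 0.2-11% of the variance of the treatment effect and mostly under 2 points of power, under assumed RDS prevalence of 50-90% and risk ratios of 1.25-3, before overlap with birth weight. The upper end needs both an even split and a risk ratio of 3. If nearly all enrolled infants have RDS, an RDS term gains almost nothing, and level of support at entry would probably vary more. The documents give no figure for how strongly either measure predicts outcome, so confidence in the exact size is low. Adjusting for the post-randomisation intermediates in (xvi) is a separate and more serious matter.

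**What to change.** - **In (xvi):** prespecify one respiratory covariate fixed before study gas starts, alongside birth weight, sex and socioeconomic status. Use either level of respiratory support at randomisation (ventilator, CPAP or nasal cannula) or RDS diagnosed before study gas. Name the choice before outcome data are seen.
- **In (xiii):** list RDS present before study gas as a baseline characteristic, not a secondary outcome.
- **State the limit:** RDS diagnosed after study gas starts is not to be used as a covariate, since it would become another post-randomisation variable.

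The cost is two wording changes and one more term in the model (two parameters if the three support levels are kept separate). Level of support needs no new data collection, because (viii) already records ventilator settings daily and (vii) ties gas delivery to the mode of support. The RDS option additionally needs a definition and a diagnosis time, which the plan does not yet contain. The main downside is a small gain, or almost none if the chosen measure hardly varies.

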(v) *Patient randomization.* Randomization will be performed as we have previously published. To keep birth-weight distribution comparable in the two groups, we will use five 250-gram-birth weight strata for randomization. To ensure equal enrollment in the two groups, infants will be randomly assigned within each stratum, according to a permuted block design to receive inhaled nitric oxide (INOmax®, INO Therapeutics) or

oxygen placebo. This strategy provides a balanced group assignment with every 4 enrollments.

(vi) *Patient enrollment at study entry procedures.* We will enroll patients and enter them into the study as we have previously published. Briefly, potential subjects will be identified, prenatally if possible, and the parents approached for informed consent. With consent obtained, and the infant born, admitted, and verified to meet inclusion criteria, a sealed envelope containing the randomized treatment assignment, appropriate identifying labels, etc., will be pulled and opened by the respiratory therapist. Documentation of the treatment assignment and patient data will be recorded by the respiratory therapist in the study book (kept in the respiratory therapy room), and an INOvent® brought to the bedside. The INOvent will be set to deliver either iNO or oxygen according to the treatment randomization and then covered to conceal the treatment group from the caregivers and investigators.

(vii) *Treatment.* iNO or placebo (oxygen) will be given 5 ppm while ventilated or on continuous positive airway pressure (CPAP) and 10 ppm while on nasal cannula oxygen. In infants receiving iNO by nasal cannula, iNO concentrations are set to 10 ppm, because previous studies have shown that delivery 10 ppm by nasal cannula results in nasopharyngeal concentrations of about 5 ppm^9. These dosages will continue until the infant no longer needs supplemental oxygen or reaches 33 weeks post conceptional age. All infants will have iNO delivery devices (INOvents) at the bedside to deliver either iNO or O2, and will be shrouded to hide from caregivers the nature of the gas being delivered. Only respiratory therapy and data safety monitor to know of gas assignments.

(viii) *Data Collection.* Clinical data (fluids, medications, diagnoses, ventilator settings) will be collected daily by our research professional.

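### Socioeconomic status is adjusted for as a confounder, but the only collection described is at the 18-month assessment, so loss to follow-up cannot be examined on it

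*Combined protocol and SAP*

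**What the plan says.** All places are in the combined protocol and SAP.

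- **Analysis.** Specific Aim #1 (xvi): "Primary outcomes will be analyzed with generalized linear models to obtain relative risks of primary outcome in the two groups". The next sentence reads "Effects of potential confounders will be adjusted for in the model: birth weight, sex, socioeconomic status", and then lists steroids, chronic lung disease, severe IVH and PVL separately as intermediates. SES is therefore treated as a confounder, on the same footing as birth weight and sex.
- **Collection.** Specific Aim #1 (xv) opens with the follow-up visit: "at 18 months post conceptional age, developmental screening with Bayley exams will be performed in our High Risk Follow-up Clinic". Within that section, after growth, vision and hearing, comes "Questionnaires assessing socioeconomic status and self report of racial ethnicity will be administered".
- **Other collection points.** At randomisation, (vi): "Documentation of the treatment assignment and patient data will be recorded by the respiratory therapist in the study book". During the stay, (viii): "Clinical data (fluids, medications, diagnoses, ventilator settings) will be collected daily by our research professional". Section (xiv) mentions a 9-month visit. None of the three names SES.
- **Prognostic weight.** Background 1: "Lower socioeconomic status (SES) also has a marked negative impact".
- **Missing data.** Section (xvi) declares an intention-to-treat analysis but gives no method for missing outcomes or covariates. The protocol does not discuss whether SES might change between birth and 18 months.

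**The concern.** A covariate used as a baseline confounder should be fixed before the outcome and known for everyone randomised. Taken at the 18-month visit, SES meets neither condition.

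First, it exists only for families who come back. The protocol expects loss of up to a fifth of survivors, in a population that (xv) calls inner-city and Appendix B calls economically depressed. SES is thus a plausible driver of loss as well as of outcome, and it is the variable one would most want for judging whether the retained infants represent those randomised. The comparison of demographic variables between groups in (xvi) could likewise cover SES only among families who return. Information not taken from a family before it is lost can rarely be recovered.

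Second, a child's disability or delay may have altered a parent's work, income or household by 18 months. Treatment is meant to change that disability, so adjusting for SES measured then could absorb a little of the treatment effect.

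**Working it through.** **1. The plan's own figure.** Section (ix) gives 82 per arm for 40% versus 20% at 80% power. Alpha is not stated; I assume 0.05 two-sided. With pooled variance under the null and no continuity correction:

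n = [1.96 × √(2 × 0.3 × 0.7) + 0.842 × √(0.4 × 0.6 + 0.2 × 0.8)]² / 0.20² = (1.270 + 0.532)² / 0.04 ≈ 81.2, rounded up to 82.

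The figure reproduces, with power 80.4% at 82 per arm. Moving the questionnaire does not change it.

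**2. How many infants would have no SES value.** Inputs: 268 enrolled, about 18% mortality and 80% follow-up from (ix); drop-out below 15% from (xiv). The 268 is taken as stated.

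| | 20% loss | 15% loss |
|---|---|---|
| Deaths: 268 × 0.18 | 48 | 48 |
| Survivors: 268 × 0.82 | 220 | 220 |
| Survivors lost | 44 | 33 |
| Assessed | 176 | 187 |
| No SES value | 92 (34%) | 81 (30%) |

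**3. What those infants cost the model.** The primary outcome in (xii) needs Bayley scores and an examination at 18 months. The infants who die and those who are lost have neither. A complete-case model of outcome on treatment and SES therefore rests on essentially the same 176 to 187 infants whether SES is taken at birth or at 18 months. What changes is the attrition analysis: for the 33 to 44 surviving infants lost, SES could not be compared with that of the retained infants, nor used in a weighting or imputation model.

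**4. Size of the reverse-causation bias.** The documents give no input for this, so the following are assumptions: SES in SD units; risk multiplied by exp(−0.3) per SD of higher baseline SES; event rates 40% and 20%, so a true relative risk of 0.50; 18-month SES equal to baseline SES minus d for infants with an abnormal outcome. A Poisson-family GLM fitted to 400,000 simulated infants gives:

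| d (SD) | SES-adjusted RR |
|---|---|
| 0 (baseline SES) | 0.50 |
| 0.1 | 0.503 |
| 0.25 | 0.513 |
| 0.5 | 0.537 |

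Varying the SES effect from 0.2 to 0.4 per SD keeps the result for d = 0.25 to 0.5 within about 0.51 to 0.54.

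**5. That bias against sampling error.** At 82 per arm,

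SE(log RR) = √[0.6 / (0.4 × 82) + 0.8 / (0.2 × 82)] = √(0.0183 + 0.0488) = 0.26,

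so the 95% interval around 0.50 is about 0.30 to 0.83. The shift to 0.513 is ln(0.513/0.50) / 0.26 ≈ 0.10 SE. The shift to 0.54 is ln(0.54/0.50) / 0.26 ≈ 0.30 SE (0.297 before rounding).

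**The case against.** - **Collection only at 18 months is inferred from silence.** The SES sentence carries no date of its own, the patient data recorded at randomisation are unspecified, and the expected demographics in (iii) include single-parent household. This stands as a limit: a reader might infer that baseline SES will not be collected, but the documents do not say so. They describe one collection point and rule out no other. The figures in (iii) are carried over from the earlier study and are not a collection plan.
- **The 81 to 92 infants are not lost because of SES timing.** This stands. A reader might infer that the adjusted analysis drops them for want of a covariate. They are absent because they have no primary outcome.
- **The bias is assumed and small.** This also stands. No document gives an effect of the child's condition on household SES, and the questionnaire is not described, so it may rest largely on stable items such as parental education. The shift runs toward the null and could not create a false benefit.
- **The SES-adjusted model may be only supportive.** Specific Aim #1, in the Specific Aims section, compares relative risks before turning to the role of other variables, and (xvii) speaks of effects persisting after adjustment. The text can be read either way. An unadjusted randomised comparison is untouched by when SES is measured.
- **Larger gaps lie nearby.** The same sentence adjusts for declared intermediates, and no missing-outcome method is given. Moving one questionnaire repairs neither, and lost infants could still be compared on birth weight, sex and nursery morbidity. That is true, but those variables do not stand in for SES.

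**Conclusion.** The point holds as a cheap improvement. As written, a variable used as a baseline confounder is collected only with the outcome, and about 81 to 92 of 268 randomised infants (30% to 34%) would have no value. The consequence that the documents support is that attrition cannot be examined or corrected on a predictor the protocol rates as strong. Reverse causation is the weaker ground: a move from 0.50 to about 0.51 to 0.54 under assumed shifts of 0.25 to 0.5 SD, which is under 0.3 of a standard error.

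The documents do not support the stronger conclusion that the primary result would be materially biased or the analysis set reduced. The verdict rests on reading the SES sentence in (xv) as dated by the visit that section describes. If SES is already recorded at enrolment, one sentence saying so settles the matter.

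**What to change.** Give the SES and race/ethnicity questionnaire to parents of every randomised infant at consent or, failing that, during the nursery stay, and add it to the data listed in (viii). State in (xvi) that the adjusted model uses this baseline value, and that the same value will be used to compare infants lost to follow-up with those retained and in any weighting or imputation for missing outcomes. Keep any 18-month SES as descriptive only.

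The cost is one short questionnaire at a contact that already takes place: (iii) has consent sought before birth or within the first 3 days. Some parents may not complete it then, which is why the nursery stay is a useful second opportunity. The sample size, treatment and visit schedule do not change. The change has to be in place before enrolment starts.
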